Sit to stand, leg press, step-up and calf raise activities will be performed under two conditions within each training session. Condition 1 will include performing two sets of ten repetitions with the targeted amount of resistance for the given session and based on rate of progression throughout training. Condition 2 will require the participant to perform as many repetitions as possible during a 20 second period utilizing either 80% of the resistance from Condition 1 or an increase in BWS of 20%. This condition is designed to encourage high velocity and hence high-power output contractions. Given our focus on muscle power generation, all participants will be instructed to perform the concentric portion of each exercise at maximum velocity regardless of the prescribed condition, followed by a controlled eccentric contraction. This approach is adapted from programs specifically targeting power training in aging populations with mobility deficits and shown to result in significant increases in peak power generation when compared to slower velocity training, while achieving similar gains in strength.^{50,51,52}

For jump training, subjects will be familiarized with the equipment and, during the initial training session, will complete a total of 30 (3 sets of 10) bilateral ground contacts (jumps). We will begin the first session at a resistance of ~20% of body mass. Based on individual subject ability, external resistance will be increased (or decreased) and resistance documented. The number of jumps will be increased to 45 in week two and to 60 thereafter (the goal being to complete the prescribed # of jumps in ≤ 3 sets). Upon successful completion of at least 60 ground contacts (e.g. complete clearance from foot plate; Figure 5), resistance will be increased in increments of 5 lbs. or 5% body mass, whichever is greatest. As subjects feel comfortable, and no later than week 4, unilateral jump training will be performed using each leg, the goal being to progress to a reciprocating jumping pattern (i.e. alternating legs each jump for a total of 60 jumps per leg). Throughout the training protocol, a minimum of two sessions at a given resistance will be required before load is increased and resistance will be held consistent between limbs throughout the training program. Session intensity will be systematically progressed and modified by changing either the applied resistance or the number of ground contacts.

Figure 5: Exercise apparatus used for jump training

Progressive loaded overground fast walking: As part of each training session, subjects will perform 10 trials of fast walking (10 meter per trial). These trials are intended to emphasize the task-specific lower extremity power generation required to accomplish increased walking speeds. Subjects will be asked to complete all trials without an assistive device or ankle-foot orthosis at speeds $\geq 125\%$ of self-selected overground velocity. Although we will

not allow the use of an AFO, subjects will be permitted to wear an ankle brace for medial-lateral support (AirCast®) that allows for plantarflexion and dorsiflexion voluntary movements. Subjects will walk over our instrumented walkway (GaitRite) so as to provide real time feedback of speed as well as spatio-temporal parameters of walking for each trial. These trials will also be performed in the ZeroG harness to protect the subject in the case of a loss of balance as well as to provide body-weight support as needed to facilitate walking at the required speeds. After each session, the average speed will be calculated and compared to the self-selected speed. When the average speed exceeds 125% of self-selected speed, we will decrease BWS by 5% for the next training session. At the point when subjects are able to successfully exceed 125% of self-selected speed without body-weight support, a weighted vest will be worn and mass systematically added to allow progression. Note that in order to provide the optimal stimulus for increasing propulsion, we will provide an amount of BWS to offset to the added mass. This has been shown to engage the muscles most responsible for generating propulsion to a greater extent⁵³ and should optimize the power training stimulus for the muscles generating propulsion.

It is important to point out that progression for muscle power training and overground stepping will be accomplished via reduction in BWS (or added mass) as tolerated, allowing for increased “resistance” and graded exercise. The overground permissive environment allows safe training without assistive devices or and allows determination of the precise ability level of the individual for a task. In creating a constant permissive environment, we are able to identify precisely how much support is required for independent completion of the task while simultaneously eliminating falls risk. This environment allows the participant to engage in therapy at a consistently more challenging level than is allowed in conventional rehabilitation. This approach is based on a philosophy known as the “challenge point framework”, which theorizes that one’s ability level is defined by the level of difficulty at which one has an equal (50%) chance of success or failure,⁴⁹ a level of difficulty that is rarely matched in clinical rehabilitation due to increased potential for falls.

Attention Control (Stretching): Stretching is being used as an attention control condition for POWER training. Control subjects will participate in a stretching protocol for the same duration (i.e. 60 minutes per session) and frequency (3 days per week) for 12 weeks to ensure that they have equal interaction with the study staff and controlling for the effects of repeated social interaction on depressive symptoms. The stretching program is a modified protocol previously implemented in a post-stroke population and designed for individuals 50 years of age and older and will include activities targeting upper and lower extremity flexibility.⁵⁴ Specifically, subjects in this group will perform traditional stretching movements targeting flexors and extensors of the knees, ankles and hips bilaterally. In addition, low back rotations, bridging, prone extensions and hip abduction will also be performed. Upper extremity movements will include shoulder flexion, horizontal flexion/abduction, internal and external rotation as well as wrist flexion and extension. As individual levels of flexibility increase, the level of difficulty will be increased accordingly. Heart rate responses to the stretching program will be intentionally kept below 40% heart rate reserve. The stretching will be overseen by a licensed physical therapist or exercise physiologist and consistently monitored throughout the period of training.

*** To provide the best care possible, those initially randomized to the control group will be offered the opportunity to re-enroll into POWER training should they still meet criteria for depression at the follow-up time point.

Dynamometric Assessment: Isometric and isotonic assessments will be performed for knee extension and ankle plantar flexion at bi-weekly intervals throughout POWER using a

Biodex isokinetic dynamometer (Biodex Corp., Shirley, NY). Prior to testing, each subject will go through a period of familiarization and warm-up consisting of 5 minutes of cycling and three sub-maximal contractions. During isometric testing, maximum voluntary isometric contraction (MVIC) will be defined as the highest torque achieved during 3 maximal contractions (~3 sec contractions separated by a minimum of 60 seconds rest). If MVIC values during the three trials differ by more than 5%, additional contractions will be performed. During isotonic testing, peak power will be assessed using 40% of MVIC. Differences in lower extremity maximal velocity are shown to occur at relatively low external forces (e.g. 40% 1 RM) and are most closely associated with gait velocity in older individuals.⁵¹ To optimize reliability of the testing, each test will be repeated 3 times. If the coefficient of variation among the 3 highest powers is > 10%, additional contractions will be performed. Power-angle curves will be plotted and the peak powers recorded. During all dynamometric testing, subjects will be instructed to (1) develop torque as fast as possible and (2) produce a maximal contraction. Subjects will be given an auditory cue and receive continuous visual feedback. All contractions will be performed with subjects positioned in the dynamometer and the axis of the dynamometer aligned with the joint axis of rotation. Proximal stabilization will be achieved with straps at the chest, hips, and knee as appropriate. In order to increase sensitivity, the force transducer signal will be amplified and fed into a data acquisition unit (Lab View Inc.) and corrected for the effects of gravity.

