Fatigue is defined as either voluntary exhaustion or inability to maintain a minimum cycling cadence of 40 RPM. Clinical criteria for termination include: 1) Hypertension: $\geq 220/120$ mmHg, or 2) Hypotension: a drop in diastolic blood pressure >20 mmHg, and O2 saturation $<85\%$. Electrocardiogram criteria include: 1) ≥ 1 mm horizontal or down sloping ST segment depression, 2) sustained paroxysmal ventricular tachycardia (>30 beats), and 3) sustained paroxysmal supraventricular tachycardia (>30 beats). If the test is terminated because of electrocardiographic findings, the subject will be managed medically as needed, referred for care, and disapproved for participation. Resting blood pressure and heart rate will be obtained prior to initiation of exercise as well as after the subject has been sitting on the stationary bicycle for 1 minute. During the exercise test, blood pressure readings will be obtained every 3 minutes. Heart rate will be obtained from the 12-lead EKG. Maximal heart rate will be recorded as the highest heart rate achieved during the exercise tolerance test.

Subject monitoring during testing and training: Blood pressure (BP) and heart rate (HR) will be monitored prior to, during, and at completion of each session. Subjects' resting diastolic BP must be <100 mmHg, systolic < 200 mmHg, and heart rate <110 beats/min to begin the testing.⁷⁴ Criteria for termination include subject complaints of shortness of breath, light-headedness, confusion, severe headache, or dyspnea; onset of angina; excessive blood pressure (systolic BP > 200 mm Hg, diastolic BP > 110 mm Hg), or drop in systolic BP > 10 mm Hg and inappropriate bradycardia (drop in heart rate > 15 bpm).

Experimental protocol for walking data collection: At the beginning of the first training session of every other week (bi-weekly), subjects will walk on a 10m. long gait mat (GaitRite) to measure self-selected and fastest comfortable walking speed and other spatiotemporal parameters. Subjects will be permitted a practice trial, and then be asked to complete three trials at each speed. For all trials, subjects will wear their own shoes and be asked to walk without an assistive device or ankle-foot orthosis. A safety harness mounted to the ceiling will protect the subject but will only support their body weight in the case of a loss of balance. A physical therapist will be present for all testing sessions as needed.

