15.0 Risks to Subjects

A licensed physical therapist will be present during all treatment sessions. In addition, during all treadmill walking trials, a safety harness will be worn to provide assistance in the event of loss of balance. The research staff will closely monitor the subject to ensure their comfort. Any adverse events will be recorded and monitored as required by our Institutional Review Board. In the event of an adverse medical event, standard facility emergency procedures will be followed and proper personnel notified. The PI on this proposal is a licensed physical therapist with several years of experience in the development and implementation of exercise interventions. Any adverse events will be recorded and monitored as required by the IRB. On-site medical services will be available in the event of adverse events to the subjects. Subjects will be able to terminate the training or testing sessions at their request at any time without prejudice. Minimization of risk will be accomplished by monitoring vital signs within prescribed criteria for termination of the training session. We will follow the American College of Sports Medicine criteria for terminating an inpatient exercise session which includes: subject complaints of light-headedness, confusion, or dyspnea; onset of angina; excessive blood pressure changes (systolic BP greater than 220 mmHg, diastolic BP greater than 110 mmHg); and inappropriate bradycardia (drop in heart rate >10 beats per minute).

At any point during the study, should a participant complete the HRSD and answer questions indicating very severe depression (>22) or answer any questions on the HRSD or PHQ-9 indicating any suicidal ideation, thoughts, or plan, they will be immediately referred for clinician evaluation. This includes those patients whose symptoms may worsen during the course of the study. A licensed psychiatrist ([name] or one of his colleagues) will be available during all depression assessments if further evaluation is necessary. In the event of an incident during treatment or training that a clinician is not immediately available, the participant will be escorted to the emergency department for further evaluation.

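### Sections 10.0 and 15.0 give different limits for ending a training session (systolic >200 vs >220 mmHg; heart-rate drop >15 vs >10 bpm), and neither section takes precedence

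*Combined protocol and SAP*

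**What the plan says.** Section 10.0, in the paragraph on subject monitoring during testing and training, gives criteria for termination. The symptoms are "subject complaints of shortness of breath, light-headedness, confusion, severe headache, or dyspnea; onset of angina". The numeric limits are "excessive blood pressure (systolic BP > 200 mm Hg, diastolic BP > 110 mm Hg"), followed by "drop in systolic BP > 10 mm Hg and inappropriate bradycardia (drop in heart rate > 15 bpm").

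Section 15.0 returns to the subject as a risk-control measure: "Minimization of risk will be accomplished by monitoring vital signs within prescribed criteria for termination of the training session". It then commits to a list: "We will follow the American College of Sports Medicine criteria for terminating an inpatient exercise session which includes". The symptoms on that list are given as "subject complaints of light-headedness, confusion, or dyspnea; onset of angina". Its blood pressure item is "excessive blood pressure changes (systolic BP greater than 220 mmHg, diastolic BP greater than 110 mmHg"). Its heart-rate item is "inappropriate bradycardia (drop in heart rate >10 beats per minute").

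Section 10.0 also has separate stopping limits for the bicycle exercise tolerance test done before inclusion, where the hypertension limit is ≥220/120 mmHg. That test is not part of the discrepancy.

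**The concern.** Both lists apply to the same sessions. One is headed as covering training, and the other speaks of ending the training session. Where they differ, staff working from one section could continue a session that the other would end, and an auditor could not say which action complied.

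The intervention is high-intensity, maximum-velocity resistance and jump training in stroke survivors, at 3 sessions a week for 12 weeks (3 × 12 = 36 planned sessions per participant). The stopping limits are therefore working safety rules. What is at stake is participant safety and consistent conduct, not the statistical inference.

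**Working it through.** The document gives no derived figure to reproduce. The check is a side-by-side comparison of the two lists.

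| Item | Section 10.0 | Section 15.0 | Result |
|---|---|---|---|
| Systolic ceiling | >200 mmHg | >220 mmHg | Differ by 220 − 200 = 20 mmHg; 10.0 stricter |
| Diastolic ceiling | >110 mmHg | >110 mmHg | Agree |
| Inappropriate heart-rate drop | >15 bpm | >10 bpm | Differ by 15 − 10 = 5 bpm; 15.0 stricter |
| Systolic drop | >10 mmHg, joined by 'and' to bradycardia | Not listed | In 10.0 only |
| Severe headache | Listed | Not listed | In 10.0 only |
| Shortness of breath | Listed, as well as dyspnea | Dyspnea only | No practical gap |
| Light-headedness, confusion, dyspnea, angina | Listed | Listed | Agree |

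Three numeric limits appear in both sections. One agrees, so 3 − 1 = 2 differ, in opposite directions.

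**Scope.** Different settings do not explain the difference, because both texts cover training. The ≥220/120 mmHg limit belongs only to the pre-inclusion bicycle test and does not account for the 220 mmHg in section 15.0.

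**Readings treated differently**, supposing no other listed stop is met:

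- Systolic above 200 and up to 220 mmHg is a listed stop in section 10.0 only.
- The heart-rate item depends on how 'and' is read in section 10.0.
  - *Joint reading* (both drops required): section 10.0 stops only when systolic falls by more than 10 mmHg and heart rate falls by more than 15 bpm. Every such case already exceeds section 15.0's 10 bpm. Section 15.0 alone therefore stops for an inappropriate fall of more than 10 and up to 15 bpm, and for a fall of more than 15 bpm without a systolic drop above 10 mmHg.
  - *Separate reading* (either drop suffices): section 15.0 alone stops for an inappropriate fall of more than 10 and up to 15 bpm when there is no systolic drop above 10 mmHg. With such a drop, both sections stop. Section 10.0 alone stops for a systolic drop above 10 mmHg without an inappropriate heart-rate fall above 10 bpm.

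**Precedence.** Neither section refers to the other, and no text ranks them.

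**The case against.** The strongest reply is that the lists can be applied together. Both are worded as open-ended, and neither tells staff to carry on below a limit. Someone who followed both would stop at whichever limit came first, 200 mmHg or 10 bpm, which is the proposed remedy. This is fair, and harm does require that one section be used alone. But open wording only permits earlier stopping. It does not say which stated number requires a stop, and no text asks staff to merge the lists item by item.

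A second reply is that 200 mmHg is plainly the working limit. Exclusion criterion 12 uses 200/110 mmHg at rest, section 10.0 requires a resting systolic below 200 mmHg to begin testing, and section 15.0 reads like carried-over text: it cites criteria for inpatient exercise and mentions treadmill walking, while the training described is overground and resistance work. The inference is reasonable for systolic pressure, but the protocol does not state it, and section 15.0 says its criteria will be followed. If section 10.0 governed throughout, the looser heart-rate limit would apply.

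Third, on the joint reading the 15 bpm figure is part of a compound criterion and not a stand-alone limit. That is correct. On that reading, though, the two heart-rate rules are further apart.

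Finally, real safeguards remain: tolerance testing with physician clearance, a licensed physical therapist at all treatment sessions, blood pressure and heart rate checked before, during and at the end of each session, shared symptom stops, and an identical diastolic limit. These reduce the risk but do not reconcile the numbers.

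**Conclusion.** The concern holds: the plan is wrong as written. Two of the three numeric limits common to both sections conflict, by 20 mmHg systolic and 5 bpm, in opposite directions, with no order of precedence. This conclusion rests on the text alone. The one open reading, how 'and' joins the two drops in section 10.0, changes which heart-rate and pressure combinations are affected but not the fact of a conflict.

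The document does not say how often readings in these bands would occur, so the practical frequency is unknown. There is no effect on the primary endpoint, sample size or error rates. It should be fixed because these are safety decision limits.

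**What to change.** Keep one list in section 10.0, covering training sessions and all testing other than the exercise tolerance test, and replace the list in section 15.0 with a reference to it. The list should:

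- use the stricter value of each numeric item: systolic >200 mmHg, diastolic >110 mmHg, inappropriate heart-rate drop >10 bpm;
- carry the combined symptoms, including shortness of breath and severe headache;
- state whether a systolic drop >10 mmHg is a stop by itself or only together with bradycardia;
- state that the exercise tolerance test keeps its own limits (≥220/120 mmHg).

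Choosing the stricter values is a clinical judgement that the document does not settle, so the study physician should confirm the list.

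The cost is amendment wording, with no added procedures. Some sessions may stop earlier, which could slightly reduce the training dose. The size of that effect cannot be estimated from the document.

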5.0 Inclusion and Exclusion Criteria/ Study Population

Subjects (male and female), ages 18-85, will be screened and recruited for the study 6-60 months following stroke. The pool of post-stroke candidates for the study will be recruited through the extensive recruiting mechanisms at the local VAMC as well as the Clinical and Translation Tools and Resources CTTR core at MUSC. All participants will have had a new ischemic stroke.

Inclusion criteria will be: 1) age 18-85; 2) stroke at least 6 months prior, 3) residual paresis in the lower extremity (Fugl-Meyer LE motor score <34); 4) ability to walk without assistance and without an AFO during testing and training at speeds ranging from 0.2-0.8 m/s; 5) no antidepressant medications or no change in doses of psychotropic medication for at least 4 weeks prior to the study (6 weeks if newly initiated medication); 6) HRSD question #9 regarding suicide <2; and 7) provision of informed consent. In addition, depressed subjects will screen for probable major depressive disorder (PHQ-9 > 10) and be diagnosed using the Structured Clinical Interview for Depression (SCID) according to the Diagnostic and Statistical Manual of Mental Disorders, Fourth Edition (DSM-IV). All subjects who meet criteria for training must complete an exercise tolerance test and be cleared for participation by the study physician.

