Post-stroke Optimization of Walking using Explosive Resistance (POWER) training: Individuals with chronic post-stroke hemiparesis will undergo training to improve muscle power generation for 12 weeks (3 times/week) that includes both resistive and task-specific elements. Session duration will be ~ 60 minutes (inclusive of rest intervals) although the total time will depend on the amount of rest needed for a given individual. Training will include five distinct resistance activities aimed at improving muscle power-- each previously reported to contribute to improved walking (Table 1). Sit to stand and leg press exercises are elements of programs shown to be effective in improving strength and walking performance in the post- stroke population.⁴⁸ Repeated step-up training using a single riser targets both eccentric and concentric training in both the sagittal and frontal planes. As possible for individual subjects, we will utilize a step height higher than standard community steps (10") to further challenge neuromuscular requirements of the task. Calf raises (i.e. plantar flexion) will be performed on a small step so as to allow for adequate range of motion. In addition, our pilot data demonstrate that jump training, focused on lower extremity muscle power generation, is part of a comprehensive program that improves gait speed in people with post-stroke gait deficits. Sit to stand, step-up and calf raise activities will be performed within the novel overground body-weight support (BWS) environment enabled by the Zero-G (ZeroG, Bioness Inc., Valencia, CA), whether receiving support or not, to provide the maximum safety possible.

During the initial training session, subjects will perform the individual component tasks beginning with least amount of BWS (or highest load) required for successful completion of

the required number of repetitions in order to match the participant's ability to the difficulty of the task.⁴⁹ BWS will be progressively reduced to determine the minimum support necessary to complete each task. Participants will be progressed within each task by decreasing BWS by 5% of body mass (or adding 5% load for leg press) upon successfully meeting the goals for progression (see Table 1). An adjustable weighted vest will be utilized to increase mass by 5% during training once support is not required for successful task completion. Subjects will not be permitted to use assistive devices and physical assistance will not be provided during training.

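### Sections 10 and 15 give different stop limits for the same training sessions (systolic >200 against >220 mmHg; inappropriate heart-rate fall >15 against >10 bpm), and no text says which prevails

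*Combined protocol and SAP*

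**What the plan says.** Section 10.0 (Study Design / Methods) has a paragraph on subject monitoring that covers both testing and training. The symptoms that stop a session are given as "subject complaints of shortness of breath, light-headedness, confusion, severe headache, or dyspnea". New angina is a further ground. For raised pressure, the paragraph gives the limit as "excessive blood pressure (systolic BP > 200 mm Hg, diastolic BP > 110 mm Hg". Its last item, on falling values, is worded "or drop in systolic BP > 10 mm Hg and inappropriate bradycardia (drop in heart rate > 15 bpm". The same paragraph sets resting limits for starting: systolic below 200 mmHg, diastolic below 100 mmHg and heart rate below 110 beats/min. These are worded as conditions for beginning the testing.

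Section 15.0 (Risks to Subjects) says risk will be minimised by "monitoring vital signs within prescribed criteria for termination of the training session". It adopts a professional society's criteria for ending an inpatient exercise session. The symptom part of that list reads "subject complaints of light-headedness, confusion, or dyspnea; onset of angina". For vital signs, the limits in that list are given as "systolic BP greater than 220 mmHg, diastolic BP greater than 110 mmHg); and inappropriate bradycardia (drop in heart rate >10 beats per minute".

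Three other provisions bear on exposure. Exclusion criterion 12 in section 5.0 removes people with severe resting hypertension (systolic >200 mmHg and diastolic >110 mmHg). Section 5.0 also says that participants "must complete an exercise tolerance test and be cleared for participation by the study physician". The tolerance test itself is stopped at 220/120 mmHg or above (section 10.0).

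**The concern.** Both lists govern training sessions, and they disagree on two of the three vital-sign limits they share. The disagreements run in opposite directions: section 10 is stricter on systolic pressure and section 15 on heart rate. Choosing one section as the authority therefore does not solve the problem. Staff who follow section 10 alone would have no stated reason to stop at a heart-rate fall for which section 15 requires it. Staff who follow section 15 alone would have none at a systolic pressure for which section 10 requires it.

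Participants are stroke survivors doing high-intensity resistance work, so this is a safety rule that should have one reading. With two, different staff could handle the same event differently, and nobody could say afterwards whether a session was run according to the protocol.

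**Working it through.** No power or sample-size figure is involved. The check sets the two lists side by side and then tests single readings against each.

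| Item | Section 10.0 | Section 15.0 | Stricter |
|---|---|---|---|
| Systolic, upper limit | >200 mmHg | >220 mmHg | Section 10 |
| Diastolic, upper limit | >110 mmHg | >110 mmHg | Equal |
| Inappropriate heart-rate fall | >15 bpm | >10 bpm | Section 15 |
| Systolic fall | >10 mmHg, joined to bradycardia by 'and' | Not listed | n/a |
| Severe headache | Listed | Not listed | n/a |

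**Scope.** Section 10's paragraph names training in its heading. Section 15 takes its criteria from an inpatient setting, but the sentence before applies them to this study's training session. The scopes overlap.

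**Systolic pressure.** The gap is 220 - 200 = 20 mmHg, that is, whole-number readings of 201 to 220. At 210 mmHg, 210 > 200 meets section 10's limit, and 210 < 220 does not meet section 15's.

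**Heart rate.** The gap is 15 - 10 = 5 bpm, that is, whole-number falls of 11 to 15. Section 10's wording has two readings, and both need checking:

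- *Either item stops a session alone.* A fall of 12 bpm with a systolic fall of 10 mmHg or less is a stop only under section 15 (12 > 10; 12 < 15). If systolic pressure has also fallen by more than 10 mmHg, section 10 stops the session too, and the lists agree.
- *Both items are required.* A fall of 12 bpm does not meet section 10 whatever the systolic pressure does. A fall above 15 bpm without a systolic fall above 10 mmHg is also a stop only under section 15.

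The statement that holds on both readings is this: an inappropriate fall of 11-15 bpm, without a systolic fall above 10 mmHg, is a stated stop only under section 15. Only falls judged inappropriate count. Sessions are described as "Session duration will be ~ 60 minutes (inclusive of rest intervals", so some decline in heart rate between sets is expected, and the plan does not say how the qualifier is applied.

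**Can the gap be reached?** The resting start limit of 200 mmHg and exclusion 12 concern pressure at rest. Neither caps pressure during exertion, and exclusion 12 as written needs both its systolic and its diastolic value. Control stretching is held under 40% of heart rate reserve (section 10.0), so the systolic gap matters mainly in POWER sessions. With 3 sessions a week for 12 weeks, each POWER participant has 3 x 12 = 36 planned sessions. The documents give no in-session readings, so the frequency of gap readings is unknown.

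**The case against.** The strongest reply is that the lists do not contradict each other. Each is introduced as what the criteria include, so neither is closed, and neither tells staff to carry on below its limit. A reading of 210 mmHg meets a stated stop in section 10, and nothing in section 15 cancels it. Read cumulatively, the two lists give the stricter limit of each pair, and the resting start limit suggests that 200 mmHg is the working systolic ceiling. This stands as a sensible way to comply. It does not remove the defect, because the protocol nowhere says the lists are cumulative and section 15 presents its own numbers as the criteria to be followed.

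The second reply is that other safeguards apply: continuous observation (section 13.0), withdrawal for persistently raised resting pressure (section 14.0), a physical therapist at every session with medical help on site (section 15.0), and physician clearance before training. These reduce the likely harm. None supplies the missing in-session number.

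Three stronger readings are tempting and should not be drawn:

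- A reader might infer that section 15 lets a session continue through severe headache or a fall in pressure, because it lists neither. Its list is open and section 10 names both, so these omissions add little.
- A reader might infer that a 12 bpm fall always separates the lists. It does so on both readings only when systolic pressure has not also fallen by more than 10 mmHg.
- A reader might take the 220/120 mmHg limit of the tolerance test as evidence for one side. That is a separate, physician-overseen, maximal-effort procedure and does not settle the limit for training.

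**Conclusion.** The concern holds as an unreconciled pair of safety limits. The systolic limits differ by 20 mmHg and the heart-rate limits by 5 bpm, in opposite directions; the diastolic limits agree. Readings of 201-220 mmHg are a stated stop only under section 10. Inappropriate falls of 11-15 bpm without a systolic fall above 10 mmHg are a stated stop only under section 15. Whether a systolic fall alone ends a session is also unclear, but that is a separate drafting ambiguity within section 10.

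This rests on both sections applying to training, as each says, and on no text setting an order between them; none was found. It should be corrected because it is a participant-safety rule and the correction is cheap. A reader might go further and infer that participants will be harmed or that the trial's results are at risk. The documents support neither: the frequency is unknown, supervision is close, and sample size and the primary analysis do not depend on these limits.

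**What to change.** Keep one list for training sessions in section 10.0 and have section 15.0 refer to it without restating numbers. Use the stricter limit of each pair: stop for systolic pressure above 200 mmHg, diastolic pressure above 110 mmHg, or an inappropriate heart-rate fall above 10 bpm, each sufficient alone. Retain onset of angina and all the section 10 symptoms, including severe headache.

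The study physician should confirm these values and state whether a systolic fall above 10 mmHg stops a session alone. The answer matters to the wording. If an inappropriate heart-rate fall above 10 bpm already stops a session, a systolic fall that counts only together with bradycardia adds nothing and can be deleted. If it counts alone, it should be a separate item.

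The cost is wording in two sections, the physician's confirmation and a briefing for session staff, with no added visits. The downside is that a few more sessions may be stopped early; how many cannot be estimated from the documents.
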